2.3.1.5 Potential risk for SAR442720 and adagrasib administration

SAR442720 is identified as a CYP3A and P-gp substrate, with CYP3A contributing to approximately 45% of total hepatocyte metabolism. Adagrasib is a strong inhibitor of CYP3A and a weak inhibitor of P-gp, which may increase SAR22720 exposure by up to 2-fold (mainly due to CYP3A inhibition). Starting dose of SAR442720 was reduced to 50% of its RP2D from monotherapy and Part-1 of this study. In addition, adagrasib will be started at the lower dose (400 mg BID rather than 600 mg RP2D).

SAR442720 is not anticipated to alter the PK of adagrasib, because SAR442720 has no effect on CYPs and transporters. Overlapping toxicities such as gastrointestinal toxicities are anticipated between the 2 drugs, hence such toxicities may occur more frequently than in the monotherapy settings. It is not known whether QT prolongation may occur more frequently with the combination therapy, however this cannot be excluded at this stage.

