E 22. Medication and supplements that may interfere or potentiate with SAR442720 and/or adagrasib metabolism or toxicity PRIOR or DURING study intervention are excluded:

- Strong CYP3A4 inducers or inhibitors (within 7 days prior)
- Strong P-glycoprotein (P-gp) inhibitors (eg, cyclosporine, tacrolimus; within 7 days prior)
- Strong Breast Cancer Resistance Protein (BCRP) inhibitors (eg, eltrombopag; within 7 days prior) (applies to Part-3 only)
- Proton pump inhibitors (within 3 days prior) or H2-receptor antagonists (within 1 day prior) during the dose escalation portion of the study
- Medications known to prolong QTc interval
- Acetylsalicylic acid (low dose aspirin, anticoagulation with low-molecular weight heparin or direct Factor X inhibitors and LMWH are allowed. Prophylactic LMWH is also allowed for high risk patients with hypercoagulability).

Diagnostic assessments

E 23. Inadequate organ and bone marrow function at the Screening visit:

- Absolute neutrophil count (ANC) $<1000 \mu\text{L} (1 \times 10^9/\text{L})$.
- Platelets $<100 \times 10^3 \mu\text{L}$ (after at least 3 days without platelet transfusion).
- Hemoglobin $<9 \text{ g/dL}$ or $<5.6 \text{ mmol/L}$ (without transfusions within 2 weeks of initiation of IMP).
- Total bilirubin $>2 \times \text{ULN}$.
- AST and/or ALT $>3 \times \text{ULN}$ (or $>5 \times \text{ULN}$ for participants with liver metastases).
- Blood creatinine $>1.5 \times \text{ULN}$ or creatinine clearance of $<50 \text{ mL/min}$ (using Cockcroft Gault formula or 24-hour urine collection)
- Prothrombin time (PT)/international normalized ratio (INR) and activated partial thromboplastin time or partial thromboplastin time (aPTT/PTT) $>1.3 \times \text{ULN}$ or outside the therapeutic range of the local laboratory if receiving therapeutic anticoagulation that would affect the PT/INR.

Other exclusions

E 24. Individuals accommodated in an institution because of regulatory or legal order; prisoners or participants who are legally institutionalized.

E 25. Participant not suitable for participation, whatever the reason, as judged by the Investigator, including medical or clinical conditions, or participants potentially at risk of noncompliance to study procedures.

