6.5.1 Prohibited concomitant therapy

In addition to prohibited medications/foods listed in Exclusion Criteria ([Section 5.2](#)), a complete list of prohibited medications during study treatment is provided in Appendix 10 ([Section 10.10](#)).

The following medications are prohibited while on study treatment:

- Medications known to prolong QTc interval
- Anti-cancer therapy (except SAR442720 and pembrolizumab or adagrasib)
- Strong CYP3A4 inhibitors and inducers
- Strong P-gp inhibitors
- Strong BCRP inhibitors (Part-3 only)
- CYP3A substrates with a narrow therapeutic index (Part-3 only)

- Proton pump inhibitors (only during the dose escalation portion of the study; for Part-3 during both escalation and expansion).
- H2-receptor antagonists (only during the dose escalation portion of the study). H2-receptor antagonist can be given at least 2 hours before and 10 hours after adagrasib (Part-3 only).
- Acetylsalicylic acid (low dose aspirin and anticoagulation with low-molecular weight heparin or direct Factor X inhibitors and LMWH are allowed. Prophylactic LMWH is also allowed for high risk patients with hypercoagulability).

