7 DISCONTINUATION OF STUDY INTERVENTION AND PARTICIPANT DISCONTINUATION/WITHDRAWAL

7.1 DISCONTINUATION OF STUDY INTERVENTION

7.1.1 Definitive discontinuation

In rare instances, it may be necessary for a participant to permanently discontinue (definitive discontinuation) study intervention. If study intervention is definitively discontinued, the participant will remain in the study to be evaluated for 30 days. See the schedule of activities (SoA; [Section 1.3](#)) for data to be collected at the time of discontinuation of study intervention and follow-up and for any further evaluations that need to be completed.

If a clinically significant finding is identified (including, but not limited to changes from baseline in QTcF) after enrollment, the Investigator or qualified designee will determine if the participant can continue in the study and if any change in participant management is needed. This review of the ECG printed at the time of collection must be documented. Any new clinically relevant finding should be reported as an AE.

Participants may stop study therapy yet continue to be monitored in the study under the following circumstances:

- A participant who experiences a Grade 4 AE, including those that meet the criteria of a DLT (ie, during Cycle 1), but is deemed by the investigator not to meet the criteria for withdrawal from the study (see below).
- Prolonged QTcF >450 msec OR change from baseline of QTcF >50 msec and that does not resolve after excluding other causes.

A participant must be discontinued from protocol prescribed therapy and removed from the study if any of the following apply:

- Documented disease progression based on RECIST v1.1
 - In certain circumstances (eg, an isolated site of progression with responses at other sites that may be amenable to localized radiotherapy), participants may be allowed to continue therapy during and after radiation with approval from sponsor Medical Monitor.
- Significant AEs leading to discontinuation of study medications
- Death
- Participant's request to withdraw from study treatment
- Ineligibility
- Unwillingness or inability to comply with study requirements
- Initiation of alternative anticancer therapy

- Investigator's decision
 - Clinical need for concomitant or other ancillary therapy that is not permitted in the study
 - Unrelated intercurrent illness that, in the judgment of the investigator, will affect assessments of clinical status to a significant degree

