10.9 APPENDIX 9: GENERAL GUIDELINES FOR THE MANAGEMENT OF ADVERSE EVENTS

Investigators must be extremely vigilant and be ready to intervene early in the management of AEs, particularly immune-related AEs because the onset of symptoms of irAEs (eg, pneumonitis) may be subtle.

- Detailed guidance for the management of specific AEs (colitis, endocrine AE, pneumonitis, renal AE, dermatologic AE, hepatitis, ophthalmologic AE [uveitis], etc.) is provided in [Table 27](#).
- General guidance is provided in [Table 26](#) below.
- If a participant experiences several AEs which involve different recommendations, the most conservative recommendation should be followed.

The recommendations provided in [Table 26](#) and [Table 27](#) should be seen as guidelines, and the treating physician should exercise clinical judgment based on the symptoms and condition of the individual participant.

Table 26 - General guidelines

Severity	Withhold/restart /discontinue SAR442720 treatment	Withhold/restart/discontinue the combination drug (Pembrolizumab or adagrasib) treatment	Supportive care
Grade 1	No action	No action	Provide symptomatic treatment.
Grade 2	No action	May delay or omit the pembrolizumab dose until Grade ≤ 1 Adagrasib dose modification/ dose interruption per Investigators discretion unless otherwise defined in Table 27 .	Consider systemic corticosteroids (Prednisone 0.5 to 1 mg/kg/day or equivalent) in addition to appropriate symptomatic treatment.
Grade 3	Delay the treatment until toxicity improves to Grade ≤ 1 or baseline.		For any Grade 3-4 immune-related adverse event, if symptoms worsen or do not improve on adequate corticosteroids (prednisone 1 to 2 mg/kg/day or equivalent) within 48 to 72 hours), consider additional immunosuppressive agents (to be selected from agents such as: infliximab, cyclophosphamide, cyclosporine and mycophenolate mofetil). Referral of the participant to a specialized unit for assessment and treatment should be considered.
Grade 4	Permanently discontinue		

Table 27 - Dose modification guidelines for combination regimens (SAR442720 and pembrolizumab combination or SAR442720 and adagrasib combination)

AE	Action

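### Table 26 offers cyclosporine as rescue for steroid-refractory immune-related events, although E22 and Section 6.5.1 prohibit it during treatment and no rescue exception is written

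*Protocol*

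**What the plan says.** **Rescue advice.** The supportive-care column of Table 26 (Protocol Appendix 9) covers Grade 3-4 immune-related events that worsen or fail to improve within 48 to 72 hours on corticosteroids. It asks the investigator to consider additional agents, "to be selected from agents such as: infliximab, cyclophosphamide, cyclosporine and mycophenolate mofetil".

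**Prohibition.** Exclusion criterion E22 (Protocol Section 5.2) covers products that may affect SAR442720 or adagrasib "metabolism or toxicity PRIOR or DURING study intervention are excluded". One of its bullets reads "Strong P-glycoprotein (P-gp) inhibitors (eg, cyclosporine, tacrolimus; within 7 days prior". Section 6.5.1 adds to the exclusion criteria its own list, opened by "The following medications are prohibited while on study treatment", and strong P-gp inhibitors are on it without restriction to a Part. That section writes exceptions for low-dose aspirin, certain anticoagulants and the timing of H2-receptor antagonists. It writes none for immune rescue.

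**Reason for the prohibition.** Section 2.3.1.5 states: "SAR442720 is identified as a CYP3A and P-gp substrate".

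**Rules that limit overlap.** For SAR442720, Table 26 says at Grade 3 "Delay the treatment until toxicity improves to Grade" 1 or baseline, and at Grade 4 it calls for permanent discontinuation. Section 7.1.1 says "A participant must be discontinued from protocol prescribed therapy and removed from the study if any of the following apply", and under the investigator's decision it lists "Clinical need for concomitant or other ancillary therapy that is not permitted in the study".

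**The concern.** One part of the protocol names a drug as an option for a serious event. Two other parts prohibit that drug because it may alter the metabolism or toxicity of SAR442720. A site following Table 26 could reasonably read the listing as permission and give cyclosporine while SAR442720 is continuing or being restarted. The participant would already be recovering from a Grade 3 or 4 toxicity, and the choice of rescue agent has to be made within two to three days. What is at stake is participant safety and protocol compliance, not the estimation of any endpoint.

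**Working it through.** No arithmetic applies. The check sets the texts side by side and asks when cyclosporine and SAR442720 could be given together.

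**Step 1: is the same drug both offered and prohibited?** Yes. Table 26 names it, E22 names it, and Section 6.5.1 prohibits its class. Section 6.5.1 does not name cyclosporine, so the link runs through E22, which that section carries forward. In Parts 1, 2 and 4 the P-gp ground is the one that applies, because the 6.5.1 bans on strong BCRP inhibitors and on narrow-index CYP3A substrates are limited to Part-3.

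**Step 2: is there a written exception, or a hold tied to cyclosporine?** No. The only interval given for P-gp inhibitors is the 7 days before study start in E22. The holds in Tables 26 and 27 depend on the grade of the event, not on the rescue drug.

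**Step 3: where can the two drugs still meet (Parts 1, 2 and 4)?**

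| Event | Instruction for SAR442720 | Overlap still possible? |
|---|---|---|
| Table 26, Grade 3 | Delay until Grade 1 or lower, or baseline | At restart, if cyclosporine is ongoing |
| Table 26, Grade 4 | Permanently discontinue | No |
| Table 27, other immune-related, Grade 3, first occurrence | Continue; withholding decided case by case | Yes |
| Same row: Grade 3-4 myocarditis, encephalitis or Guillain-Barre syndrome; all Grade 4; recurrent Grade 3 | Permanently discontinue both drugs | No |
| Table 27, hyperthyroidism Grade 3 or higher | Continue | Yes |
| Table 27, colitis Grade 3, first occurrence | Withhold until Grade 0 to 1 | At restart |
| Table 27, pneumonitis Grade 3-4 | Withhold; may restart lower at Grade 1 or below | At restart |
| Table 27, skin Grade 4 | One line holds and resumes two levels lower; another discontinues | At restart, on the first line |
| Table 27, liver Grade 4 | Hold; restart at reduced dose if resolved | At restart |

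Restarting during cyclosporine would still breach Section 6.5.1, but none of the restart instructions says so.

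**Step 4: does Section 7.1.1 close these routes?** If applied, yes: the participant leaves study therapy, so there is neither continuation nor restart. It applies only if the investigator recognises cyclosporine as non-permitted, and the Table 26 listing points the other way. Its outcome also differs from the delay and restart that Table 26 sets for a Grade 3 event.

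**The case against.** The strongest reply is that nothing compels a site to break a rule. Table 26 says to consider agents and gives four examples. Appendix 9 calls Tables 26 and 27 guidelines subject to clinical judgment, whereas E22 and Section 6.5.1 are prohibitions. A site that chooses infliximab or mycophenolate mofetil complies with all of them. Section 6.5 sends questions on concomitant therapy to the Medical Monitor, Appendix 10 asks sites to consult prescribing information, and Section 7.1.1 removes a participant who needs non-permitted treatment. All of this stands, and it keeps the point minor. It does not explain why a prohibited drug should be among the examples.

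Some stronger readings should be resisted:

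- A reader might infer that the protocol directs a prohibited drug, or that overlap is the usual result. Table 26 only offers it, and most cases are held or discontinued.
- A reader might infer a sizeable rise in exposure from the increase of up to 2-fold in Section 2.3.1.5. That figure concerns adagrasib and is attributed mainly to CYP3A inhibition. The documents give no figure for a strong P-gp inhibitor.
- A reader might call it an error that the strong P-gp list in Appendix 10 omits cyclosporine and tacrolimus. The appendix calls itself partial and not comprehensive, and it lists both drugs under other classes.
- A reader might extend the point to cyclophosphamide, which Table 26 also names. It sits in Appendix 10 as a narrow-index CYP2B6 substrate, and Section 6.5.1 refers to that appendix for the prohibited medications. Its absence from the 6.5.1 bullets therefore does not show that its status is open, and this point does not rest on it.

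**Conclusion.** The inconsistency holds and is minor. The protocol lists as a rescue option a drug that it prohibits by name in E22 and by class in Section 6.5.1, with no exception. The practical gap is confined to Parts 1, 2 and 4. It covers the two Table 27 situations in which SAR442720 continues (first-occurrence Grade 3 other immune-related reactions outside the three named exceptions, and hyperthyroidism of Grade 3 or higher) and the restarts governed by toxicity grade alone.

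This rests on two assumptions: that cyclosporine is the agent chosen, and that the site takes the Table 26 listing as permission and so does not invoke Section 7.1.1. The documents give no frequency for such events. No endpoint, sample size or analysis is affected.

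**What to change.** Delete cyclosporine from the example agents in Table 26. Infliximab and mycophenolate mofetil remain, and neither appears in Appendix 10. This removes the conflict without changing E22, Section 6.5.1 or any restart rule. The cost is a wording change and one fewer example rescue agent.

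Keeping cyclosporine would be harder. It would need an exception in both E22 and Section 6.5.1 and a hold of SAR442720 with a stated interval before restart. The documents do not supply that interval: the 7 days in E22 is a washout before entry, and nothing supports using it as a restart rule.

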Skin reactions	
Grade 1 or 2 (tolerable): Administer supportive care and continue study drugs
 
Intolerable Grade 2-Grade 3: Hold both drugs until < Grade 2. If improves to < Grade 2 within 4 weeks, then reduce SAR442720 by one dose level and resume combination drugs at the same dose level.
 
Suspected Stevens-Johnson Syndrome (SJS) or toxic epidermal necrolysis (TEN): Withhold both drugs until adverse reactions recover to Grade 0-1.
 
Grade 4: Hold both drugs until < Grade 1. If improves to < Grade 1 within 4 weeks, resume, reduce SAR442720 by two dose levels and resume combination drugs at the same dose level.
 
Grade 4 or confirmed SJS or TEN: Permanently discontinue both drugs
 
If \geq Grade 3 rash recurs despite two SAR442720 dose level reductions, permanently discontinue both drugs.
 
If rash does not improve within 4 weeks, permanently discontinue both drugs.

Ocular symptoms > Grade 2	
Hold both study drugs and obtain ophthalmology consult.
 
RVO: Any grade, permanently discontinue both drugs (Part-1, 2, and 4 only). In Part-3 permanently discontinue SAR442720 but may continue adagrasib, please consult with the Medical Monitor.
 
Neurosensory retinal detachment: Hold both drugs until resolution to \leq Grade 1. If resolves within 4 weeks, then reduce SAR442720 by one dose level. If visual symptoms > Grade 2 recur despite two dose level reductions, permanently discontinue both drugs. (Part-1, 2 and 4 only). In Part-3 permanently discontinue SAR442720 but may continue adagrasib, please consult with the Medical Monitor.
 
Uveitis/iritis > Grade 2: Hold both study drugs. If resolves to \leq Grade 1 within 4 weeks, then reduce SAR442720 dose by one level and resume both study drugs. If recurs despite two dose level reductions of SAR442720, permanently discontinue both drugs. If > Grade 1 symptoms recur or follow-up ophthalmology examination results worsen, withhold treatment (either SAR442720 and pembrolizumab or SAR442720 and adagrasib) and either further decrease dose or permanently discontinue treatment.
 
Other > Grade 2 AE: Hold SAR442720. If AE doesn't improve within 2 weeks, then consider holding the combination drug. If no improvement within 4 weeks from onset, consider permanently discontinuing both drugs. In ambiguous cases, please consult with the Medical Monitor.

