Hepatitis, liver function test abnormalities (AST, ALT, and/or total bilirubin)	
Grade 1: Continue both study drugs at current doses.
 
Grade 2: In Part-1, 2, and 4, continue SAR442720 and withhold pembrolizumab until adverse reactions recover to Grade 0 to 1
 
In Part-3, continue SAR442720 and reduce adagrasib one dose level.
 
Grade 3: Rule out other causes such as metastatic liver disease, concomitant drugs, infection, etc. Withhold both study drugs until improves < Grade 1, then dose reduce SAR442720 and adagrasib one dose level (in Part-3) and resume pembrolizumab at the same dose (Part-1, 2 and 4). If AE does not improve or recurs, dose reduce another dose level of SAR442720. No dose modification required for isolated GGT. In Part-1, 2, and 4 hold SAR442720; if no improvement in LFTs after SAR442720, withhold pembrolizumab as well. If Grade ≥ 3 with AST or ALT occurs, permanently discontinue both study drugs.
 
In case of liver metastasis with baseline Grade 2 elevation of AST or ALT, hepatitis with AST or ALT increases $\geq 50\%$ and lasts ≥ 1 week: Permanently discontinue pembrolizumab. Action with SAR442720 or adagrasib should be discussed with the Medical Monitor.
 
Grade 4: see general Grade 4 non-heme AEs. In Part-1, 2, and 4 hold both SAR442720 and pembrolizumab. If resolves, restart both medications, SAR442720 at reduced dose (pembrolizumab dose reduction is not allowed). If no improvement to < Grade 1 within 4 weeks, permanently discontinue both drugs.
 
In Part-3 permanently discontinue both study drugs. Concurrent treatment-emergent / treatment related elevation of AST or ALT $> 3 \times$ ULN AND total bilirubin $> 2 \times$ ULN or INR > 1.5 in the absence of cholestasis and other causes (eg, viral hepatitis, other pre-existing or acute liver disease, or another drug capable of the observed injury), which may indicate severe drug-induced liver injury (possible Hy's law case). Both medications should be permanently discontinued.
 
If liver injury is due to other causes such as viral hepatitis, acute liver disease, or another drug capable of liver injury, evaluate the extent of liver injury (eg, albumin level, PTT, INR etc) and if considered to be severe, discontinue both medications.

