QTcF prolongation	
Rule out other factors for arrhythmia including myocardial ischemia, electrolyte abnormalities, and concomitant medications. Evaluate concomitant medications that prolong QTcF (eg, 5-HT3 receptor antagonist anti-emetics etc) and discontinue the suspected concomitant medication, as feasible. Hold discontinue both study drugs per below instructions. Consult cardiology.
 
Grade ≥ 3: Hold both study drugs until QTcF < 480 msec; correct electrolytes; consult cardiology. If resolves within 4 weeks, restart both drugs; SAR442720 and adagrasib at one dose level lower (pembrolizumab dose reduction is not allowed); otherwise permanently discontinue.
 
Repeat ECG at 2 weeks and 4 weeks after restarting. Perform additional ECGs monitoring at D15 of each subsequent cycle for 3 cycles then as instructed by the SoA. For recurrence of QTc prolongation follow the guidelines above and reduce dose of SAR442720 and adagrasib by another dose level (pembrolizumab dose reduction is not allowed). Permanently discontinue both SAR442720 and pembrolizumab if after correction of associated risk factors and dose reductions, the QTcF increase meets values of both > 500 msec and > 60 msec change from pre-treatment values.
 
In Part-3: If QTcF Prolongation* > 500 msec and increases by > 60 msec on at least 2 ECGs ≤ 22 days, hold adagrasib until \leq Grade 1 or return to baseline (< 15 msec above baseline). Resume adagrasib at one or two dose levels lower. If QTcF Prolongation* > 500 msec and increases by > 60 msec on at least 2 ECGs > 22 days, discontinue adagrasib.

AE	Action

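### Table 27 gives two opposite instructions for a Grade 4 skin reaction; less firmly, several Table 27 entries assume a second SAR442720 reduction that Section 6.6 does not state for Part-2

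*Protocol*

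**What the plan says.** **Grade 4 skin reactions.** Table 27 (Protocol Appendix 9, Section 10.9) has two consecutive lines.

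- The first holds both drugs. If the reaction falls below Grade 1 within 4 weeks, the site is to "resume, reduce SAR442720 by two dose levels and resume combination drugs at the same dose level".
- The second says "Grade 4 or confirmed SJS or TEN: Permanently discontinue both drugs".

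The introduction to Appendix 9 presents Table 26 as general guidance and Table 27 as the detailed guidance for specific events. It calls both guidelines, to be applied with clinical judgment. It also says to follow the most conservative recommendation when a participant has several adverse events that point different ways.

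**Number of SAR442720 reductions.** Section 6.6 treats the parts in separate paragraphs. The allowance of two reductions closes the paragraph on the dose escalation cohorts. The Part-2 paragraph permits reduction according to criteria given later in the section, and then describes a reduction to the dose one step below the RP2D. It gives no number of reductions.

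These Table 27 entries assume more than one step:

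- Neurosensory retinal detachment: if visual symptoms "recur despite two dose level reductions, permanently discontinue both drugs. (Part-1, 2 and 4 only".
- QTcF prolongation, on recurrence: "reduce dose of SAR442720 and adagrasib by another dose level (pembrolizumab dose reduction is not allowed".
- Rash of Grade 3 or more: if the "rash recurs despite two SAR442720 dose level reductions, permanently discontinue both drugs".
- Uveitis/iritis: "If recurs despite two dose level reductions of SAR442720, permanently discontinue both drugs".

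**The concern.** Protocol Section 10.3.3 treats Grade 4 as life-threatening, and Section 2.3.1.2 lists SJS and TEN among the pembrolizumab warnings. A site that follows the first skin line can restart SAR442720 at a lower dose and the combination drug at its previous dose. A site that follows the second never restarts either. The detailed table is where a site would look for the answer, and it gives both.

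On the second matter, a Part-2 site that reads Section 6.6 sees one step down. If it reads Table 27, it finds recurrence rules that count two. Sites could therefore differ on whether a second reduction is available, and on when a recurrence means stopping.

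**Working it through.** No sample size, power or other computed figure is involved. The check is a comparison of texts, plus a count of steps on the dose ladder.

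**Step 1: do the two skin lines conflict?** The trigger is the same, a Grade 4 skin reaction. The actions are hold with possible rechallenge, and permanent discontinuation. Neither line carries a part label or a drug restriction. The footnote to Table 27 defines both study drugs as whichever pair the part uses, so both lines apply in every part.

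**Step 2: can the second line be read as Grade 4 SJS or TEN only?** That reading is possible, but it is not what the words say. The hemorrhage and colitis rows build their stopping lines the same way, with Grade 4 as a condition in its own right joined by *or* to another.

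**Step 3: does other text settle it?**

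- The most-conservative rule is written for several events in one participant, not for two instructions on one event.
- Table 26 calls for permanent discontinuation at Grade 4 and so favours the second line. It does not override Table 27 automatically, because other Table 27 rows allow restart after Grade 4: cytopenias, other non-hematologic events, and liver abnormalities in Parts 1, 2 and 4.
- The row for other immune-related reactions stops both drugs at Grade 4, but only for immune-related events and only in Parts 1, 2 and 4.
- The ocular, hemorrhage and colitis rows refer ambiguous cases to the Medical Monitor. The skin row does not.

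The balance leans towards stopping, but the row itself remains contradictory.

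**Step 4: the Part-2 dose steps.** The inputs are the Part-2 RP2D of 200 mg BIW (Section 4.1, Part-2) and the Part-1 ladder of 200, 140 and 100 mg BIW (Table 13).

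- One step below: 200 → 140 mg. Section 6.6 does not print this dose for Part-2; it is inferred.
- Two steps below: 200 → 140 → 100 mg.
- Difference: 140 − 100 = 40 mg per dose.

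**Step 5: which entries reach Part-2?** Retinal detachment is the clearest, because its label names Part-2. The QTcF row reaches Part-2 because it rules out reducing pembrolizumab; its first event already costs one level, so another level is a second. The rash and uveitis rules carry no part label. That makes four wordings in three rows. The Grade 4 skin resume line would also take a Part-2 participant down two levels, to 100 mg, for as long as it stays in the table.

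**The case against.** The strongest reply concerns the dose-reduction point. Section 6.6 does not say that one step is the most Part-2 allows, and it points forward to criteria that lead to Table 27. Table 27 could therefore be what supplies the second step. This reply largely stands. The text shows a gap and a mismatch, not a proven prohibition.

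A reader might be tempted to go further in four ways that the documents do not support:

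- **A firm Part-2 cap of 140 mg.** The dose is inferred, and the wording is permissive.
- **A longer list of conflicts.** The liver sentence, "If AE does not improve or recurs, dose reduce another dose level of SAR442720", may continue the Part-3 reduction that precedes it. The uveitis line that offers to "either further decrease dose or permanently discontinue treatment", like the similar sentence in Section 6.6.1.3, lets a site comply with both texts by stopping.
- **Stopping rules that cannot operate in Part-2.** Other routes exist. Rash that does not improve within 4 weeks stops both drugs, recurrent Grade 3 immune-related reactions do the same, and Section 7.1.1 allows discontinuation for significant adverse events or by investigator decision.
- **A Part-3 reduction with no reference dose.** Table 14 prints the Part-3 ladder, and one level below can naturally be read as below the assigned level.

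On the skin lines, the reply is that the tables are guidelines subject to clinical judgment, and that rechallenge requires near-complete recovery. Both statements are true. Judgment helps a physician apply a recommendation; it does not reconcile two opposite ones.

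**Conclusion.** The Grade 4 skin conflict holds on the printed text: one row, one trigger, two incompatible actions. This conclusion needs no assumption beyond reading the second line as written.

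The Part-2 point holds in a softer form and with lower confidence. Section 6.6 describes one step and states the two-reduction allowance only for dose escalation, while four Table 27 wordings that reach Part-2 presume a second step. Where that step is taken, the dose is 100 mg rather than 140 mg, assuming the Part-1 ladder applies.

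The number of participants affected cannot be estimated, because the documents give no rates for these events under the combination. No statistical figure is affected. This is a correction to safety instructions that should be made.

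**What to change.** 1. **Skin reactions row.** Keep one Grade 4 instruction. The default is to delete the hold-and-resume line, which brings the row into line with Table 26. If the sponsor intends rechallenge after Grade 4 reactions other than SJS or TEN, limit the stopping line to confirmed SJS or TEN. That choice is clinical and belongs to the sponsor.
2. **Section 6.6, Part-2 paragraph.** State the maximum number of SAR442720 reductions, and preferably print the lowest dose: 140 mg if one reduction is allowed, 100 mg if two.
3. **Table 27.** Align the retinal detachment, QTcF, recurrent rash and uveitis wordings with that number. If the Grade 4 skin resume line is kept, align its two-level drop as well.

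The cost is protocol wording only. Sample size, endpoints and planned analyses do not change.
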